**Table 6. Study CO-338-097 Schedule of Assessments**

	Screening Phase	Treatment Phase a (±3 days of scheduled timepoint)						Post-treatment Phase			
		Cycle 1			Cycle 2		Cycle 3+	EOT	FU-28 28 ±3 d after last oral/IV dose	FU-100 100 +7 d after last IV dose	LTFU
Procedure	D-28 to D-1 b	D1 c,d	D15 e	D28	D1 d	D15 d	D1 d				

least 18 months, may decrease the frequency of disease assessments to every 12 calendar weeks (±7 days). Tumor assessments should continue as per protocol even if dosing is delayed.

- s = Disease assessments should also be done at the time of treatment discontinuation if it has been ≥ 8 weeks since the last assessment.
  - t = If treatment was discontinued for reasons other than radiologic disease progression or death, radiologic tumor assessment (using the same methodology as was used at initial study screening) will continue until confirmed radiographic disease progression, death, or initiation of subsequent treatment. Assessment at 12-week (±7days) intervals from Cycle 4 Day 1 for the first 18 months after initiation of study treatment, and every 24 weeks (±14 days) thereafter, until objective radiological disease progression by RECIST v1.1, as assessed by the investigator, is documented.
  - u = A mandatory biopsy or resection of tumor tissue must be collected ≤ 42 days prior to first dose of rucaparib. Alternatively, tumor tissue collected > 42 days prior to the first dose of rucaparib may be submitted, provided there have been no intervening anticancer treatments during this period and the tissue is of adequate quality. Tumor tissue samples should be from primary or metastatic tissue. Patients may be enrolled prior to tumor tissue being analyzed by the central laboratory, provided there is confirmation that the tumor tissue has been received by the central laboratory
- Tumor tissue must be obtained from a soft tissue tumor lesion; ascites is not acceptable. Refer to the Laboratory Manual for detailed sample handling instructions.
- v = An additional mandatory biopsy will be collected at Cycle 1 Day 28 (-5 days), unless tumor biopsy procedure is contraindicated (eg, unacceptable risk in the opinion of the investigator). This additional biopsy will be collected prior to commencement of nivolumab on Cycle 2 Day 1 (= Cycle 1 Day 28 [window:-5 days]). Tumor tissue must be obtained from a soft tissue tumor lesion; ascites is not acceptable. Refer to the Laboratory Manual for detailed sample handling instructions.
  - w = An optional post-treatment tumor biopsy sample may be collected from patients who progress on study treatment. If the progression is due to new lesions, the preference is to obtain the biopsy from the new lesion(s). Additional consent is required. Refer to the Laboratory Manual for detailed sample handling instructions.
  - x = Refer to [Table 8](#) and [Table 9](#), and the Laboratory Manual for detailed sample collection and processing instructions. Cycle 1 ctDNA must be collected even if within 3 days of screening ctDNA.
  - y = Nivolumab administration will commence on Cycle 2 Day 1.

**Table 6. Study CO-338-097 Schedule of Assessments**

	Screening Phase	Treatment Phase a (±3 days of scheduled timepoint)						Post-treatment Phase			
		Cycle 1			Cycle 2		Cycle 3+	EOT	FU-28 28 ±3 d after last oral/IV dose	FU-100 100 +7 d after last IV dose	LTFU
Procedure	D-28 to D-1b	D1c,d	D15e	D28	D1d	D15d	D1d				

z = A single sample should be collected as close as possible to 12 hours after the last dose has been taken and prior to the next dose. Refer to the Laboratory Manual for sample collection and processing instructions.

aa = Refer to PK sampling [Table 7](#).

ab = All patients discontinued from treatment, regardless of reason, should be followed for survival and subsequent therapies every 12 weeks (±14 days) until death, loss to follow-up, withdrawal of consent from study, or study closure, whichever happens first. Follow-up can be performed via the telephone.

**Table 7. Pharmacokinetic and Immunogenicity Sample Collections**

Study Day (Cycle, Day) a (1 Cycle = 28 days)	Time (Event)	Time (Relative to Start of Infusion)	Pharmacokinetic Blood Sample for Nivolumab	Immunogenicity Blood Sample for Nivolumab	Pharmacokinetic Blood Sample for Rucaparib b
C2D1	(Predose) c	00:00	X	X	X
	(EOI) d	00:30	X		
C3D1	(Predose) c	00:00	X		X
C4D1	(Predose) c	00:00			X
C6D1	(Predose) c	00:00	X	X	X
CXD1: Every 4 cycles after C6 D1 (ie, C10D1, C14D1, etc.)	(Predose) c	00:00	X	X	
Safety Follow-up Visits, FU-28 and FU-100 (28 days and 100 days, respectively, from the treatment discontinuation during the Treatment Phase or at 24 months)	NA	NA	X	X	

Abbreviations: EOI = end of infusion; FU-100 = 100-day Follow-up Visit after last dose of IV study drug; FU-28 = 28-day Follow-up Visit after last dose of study drug (oral or IV, whichever is later); NA = not applicable; PK = pharmacokinetic.

- a = If a patient discontinues study drug treatment during the sampling period (ie, prior to 24 months), all subsequent CXD1 samples will be inapplicable, but samples will be collected on FU-28 and FU-100 for nivolumab PK and immunogenicity analysis.
- b = PK samples for rucaparib are to be collected approximately 12 hours after the last dose, but prior to the next dose (ie, within 1 hour). If dosing is held for toxicity or any other reason, PK sample should still be collected at the end of treatment Cycles 1, 2, 3, and 5.
- c = All predose samples for nivolumab should be taken (preferably within 30 minutes) prior to the start of nivolumab infusion. If it is known that a dose is going to be delayed, then the predose sample should be collected just prior to the delayed dose. However, if a predose sample is collected but the dose is subsequently delayed, an additional predose sample should not be collected.
- d = EOI-nivo: **EOI samples should be collected immediately (preferably within 5 minutes) prior to stopping nivolumab infusion.** If the end of infusion is delayed, the collection of the EOI samples should be delayed accordingly. Please ensure accurate collection of time/date of sample collection. EOI samples may not be collected from the same IV access as drug was administered.

**Table 8. Peripheral Blood Biomarker Sample Collection**

Study Day (Cycle, Day) (1 Cycle = 28 days)	Time	Genomic DNA from blood	Immunophenotyping (PBMC)	Neo-epitope DNaseq	Serum cytokine/ chemokine profiling
C1D1	Predose	X	X	X	X
C2D1	Predose		X	X	X
C5D1	Predose		X	X	X
C7D1	Predose			X	X
C9D1	Predose			X	X
Upon Disease Progression	N/A		X	X	X

Abbreviations: DNaseq = deoxyribonucleic acid sequencing; N/A = not applicable; PBMC = peripheral blood mononuclear cells.

**Table 9. Blood Sample Collection for ctDNA**

Blood for ctDNA Plasma	Screening	Predose				Upon Disease Progression	Safety Follow-up Visits, FU-28 and FU-100 b
		C1D1	C2D1	C3D1	CXD1 a		
Cohort A	X	X	X	X	X (starting with C4)	X	X

Abbreviations: ctDNA = circulating tumor DNA; FU-100 = 100-day Follow-up Visit after last dose of IV study drug; FU-28 = 28-day Follow-up Visit after last dose of study drug (oral or IV, whichever is later).

a = After cycle 3, collect blood for ctDNA at every other cycle from the start of the oral/IV combination treatment on Cycle 2 Day 1 for Cohorts A1/A2.

b = FU-28 and FU-100, 28 days and 100 days, respectively, from the treatment discontinuation during the Treatment Phase or at 24 months

## 7.2 Informed Consent

The investigator or their designee shall discuss with each patient the nature of the study and its requirements. To participate in the study, informed consent must be obtained from each potential patient prior to any study activities. The information on the IRB/IEC-approved consent form should be translated and communicated in the language the patient (or legally-authorized representative) can understand. A separate consent form may be used for tissue testing.

Analysis of tumor tissue for a deleterious BRCA1/2 mutation (germline or somatic) will be performed using the Foundation Medicine's NGS test (germline/somatic status will not be differentiated in the test report). These results will be provided to patients who consent to receive this information. In the event a BRCA1/2 alteration is identified in tumor tissue, the patient may be referred by the investigator for genetic counseling and potential germline testing per institutional guidelines. If mutations other than BRCA1/2 are identified by the NGS test, they will also be provided to patients who consent to receive this information when they discontinue from treatment.

Additionally, patients participating in the optional tumor tissue biopsy at the time of radiographic disease progression/ treatment discontinuation must provide additional consent for this procedure.

All procedures and assessments are to be completed within  $\pm 3$  days of the scheduled time unless otherwise stated.

## 7.3 Screening Phase

Following written informed consent, and unless otherwise specified, the following assessments will be performed prior to enrollment within the allowable windows of time as indicated below. Assessments performed within the specified windows, but prior to patient signing informed consent, are acceptable to be used as a study procedure only if confirmed to have been standard of care. Screening procedures may be repeated if the findings/results are considered invalid or not representative of the patient's baseline medical status. When screening procedures are repeated, the rationale should be documented in the source file.

Consent may be completed outside the 28-day screening window as consent does not expire. Reconsent is not required if outside the screening window. The screening period begins with the first study-specific procedure, performed outside standard of care, and only after consent for study participation has been provided.

### 7.3.1 Up to 42 Days Prior to Start of Treatment

A mandatory biopsy or resection of tumor tissue must be collected  $\leq 42$  days prior to first dose of rucaparib. Alternatively, tumor tissue collected  $> 42$  days prior to the first dose of rucaparib may be submitted, provided there have been no intervening anticancer treatments during this period and the tissue is of adequate quality. Tumor tissue samples should be from primary or metastatic tissue. Patients may be enrolled prior to tumor tissue being analyzed by the central laboratory, provided there is confirmation that tumor tissue is available to be sent to the central laboratory.

Tumor tissue must be obtained from a soft tissue tumor lesion; ascites is not acceptable. Refer to the Laboratory Manual for detailed sample handling instructions. See [Section 7.5.6.1](#) for central laboratory analysis.

### 7.3.2 Up to 28 Days Prior to Start of Treatment

- Medical/oncology history, including demographic information
- Physical examination by body system, including height and weight
- Vital signs (blood pressure, pulse, and body temperature)
- SAE monitoring (only report if related to screening procedure)
- Prior and concomitant medications, any surgical/medical procedures
- 12-lead ECG (Local)
- Tumor assessment: assessments should consist of clinical examination and appropriate imaging techniques (preferably CT scans of the chest, abdomen, and pelvis with appropriate slice thickness per RECIST v1.1). Other assessments (MRI, X-ray, positron emission tomography [PET], and ultrasound) may be performed if required. The same methods used to detect lesions at baseline are to be used to follow lesions throughout the clinical study.
- If a patient has known brain metastases, this disease should be evaluated at each required assessment time
- Collect ctDNA blood sample (Central)

### 7.3.3 Up to 14 Days Prior to Start of Treatment

- ECOG performance status ([Appendix 3](#))
- SAE monitoring (only report if related to screening procedure)
- Hematology (Local)
- Clinical chemistry (Local). Note: fasting is not required
- Urinalysis (Local) (performed on freshly voided clean sample)
- Serum pregnancy test for women of childbearing potential (must be completed  $\leq 3$  days prior to the first dose of rucaparib)
- CA-125 Measurement (Local)

## 7.4 Treatment Phase

### 7.4.1 Cycle 1 Day 1

The following procedures will be completed before the first dose of rucaparib is administered, unless if completed  $\leq 3$  days prior to the first dose of rucaparib in which case they may be omitted, IV nivolumab will be administered after the first dose of rucaparib:

- Physical examination
- Weight
- ECOG performance status ([Appendix 3](#))
- Vital signs
- Concomitant medications and any surgical/medical procedures
- Hematology (Local)
- Clinical chemistry (Local) (fasting is not required)
- Serum pregnancy test for women of childbearing potential (Local)
- Urinalysis (Local)
- Collect ctDNA blood sample (this sample **must** be collected even if a sample was collected within 3 days prior to the first dose of rucaparib)
- CA-125 Measurement (Local)
- Blood sample for genomic analysis (Central) (If sample is not collected on Day 1 of Cycle 1, it should be collected as soon as possible thereafter)
- Blood sample for immunophenotyping (peripheral blood mononuclear cells [PBMC])
- Blood sample for neo-epitope DNA sequencing (DNaseq)
- Blood sample for cytokine/chemokine profiling
- AE monitoring
- Dispensation of rucaparib

Rucaparib tablets will be dispensed to the patient in sufficient quantity to last until the next rucaparib dispensation visit, with a small overage. Patients will ingest rucaparib twice daily at about the same times every day as close as possible to 12 hours apart. Rucaparib should be taken with water and with or without food. Patients will keep all unused tablets and containers (empty, partially used, and/or unopened) and return with them to the study site for accountability at the next visit. Nivolumab IV will be administered as described in the Pharmacy Manual. In the event of toxicities, re-treatment or dose modification will be according to the criteria described in [Table 4](#).

Site personnel will account for all rucaparib that is administered or dispensed to the patient during the study visit and document appropriately.

#### 7.4.2 Cycle 1 Day 15

Patients will be instructed to refrain from taking their first dose of rucaparib at home on the day of their visit. The following procedures will be completed prior to rucaparib dosing and  $\pm 3$  days of this visit. IV nivolumab will be administered after rucaparib.

- Physical examination
- Weight
- Vital signs
- Concomitant medications and any surgical/medical procedures
- Hematology (Local)
- Clinical chemistry (Local) (fasting is not required)
- Urinalysis (Local)
- AE monitoring

#### 7.4.3 Cycle 1 Day 28

A mandatory tumor tissue biopsy will occur on C1D28 (window: -5 days) prior to commencement of IV study medication (See [Section 7.5.6.1](#)).

#### 7.4.4 Cycle 2 Day 1

Patients will be instructed to refrain from taking their first dose of rucaparib at home on the day of their visit to collect plasma samples for PK and the ctDNA blood sample.

Plasma samples for PK analysis should be collected before the morning dose as close as possible to 12 hours after the previous dose. If the start of the next dose is delayed, the PK sample should still be collected during this visit instead of the delayed start of the next study visit.

The following procedures will be completed before the morning dose of rucaparib is administered and may be performed  $\pm 3$  days of this visit. IV nivolumab will be administered after rucaparib.

- Physical examination
- Weight
- ECOG performance status ([Appendix 3](#))
- Vital signs
- Concomitant medications and any surgical/medical procedures
- Hematology (Local)
- Clinical chemistry (Local) (fasting is not required)
- Serum pregnancy test for women of childbearing potential (Local)
- Urinalysis (Local)
- Collect ctDNA blood sample (Central) – Reduced volume collected at this visit. Please see Laboratory Manual for details.

- CA-125 Measurement (Local)
- PK sample collection (Central) - according to [Table 7](#)
- Blood sample for immunophenotyping (PBMC)
- Blood sample for neo-epitope DNAseq
- Blood sample for cytokine/chemokine profiling
- AE monitoring
- Patients return all unused tablets and containers (empty, partially used, and/or unopened) to the study site for accountability
- Dispensation of rucaparib
- Administration of IV nivolumab (after the morning dose of rucaparib)

Patients will ingest rucaparib twice daily at about the same times every day as close as possible to 12 hours apart. Rucaparib should be taken with water and with or without food. Nivolumab IV will be administered as described in the Pharmacy Manual. In the event of toxicities, re-treatment or dose modification will be according to the criteria described in [Section 5.5](#).

#### 7.4.5 Cycle 2 Day 15

Patients will be instructed to refrain from taking their first dose of rucaparib at home on the day of their visit. The following procedures will be completed before the morning dose of rucaparib is administered and may be performed  $\pm 3$  days of this visit. IV nivolumab will be administered after rucaparib.

- Physical examination
- Weight
- Vital signs
- Concomitant medications and any surgical/medical procedures
- Hematology (Local)
- Clinical chemistry (Local) (fasting is **not** required)
- Urinalysis (Local)
- AE monitoring

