## 5.3 Method of Assigning Patients to Treatment Groups

All patients enrolled in the study will receive oral rucaparib at an initial dose of 600 mg BID continuously commencing C1D1, and IV nivolumab at an initial dose of 480 mg Q4W commencing C2D1.

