#### 5.4.2 Nivolumab

Nivolumab is administered as 480 mg via a 30-minute IV infusion on Day 1 of every 28-day cycle, starting on **Cycle 2 Day 1**. IV study drug infusion should be prepared as specified in the Pharmacy Manual. Refer to the current version of the IB and/or Pharmacy Manual for complete storage, handling, dispensing, and infusion information.

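### Visit text for Cycle 1 Day 1, Cycle 1 Day 15 and Cycle 2 Day 15 says nivolumab is given, contradicting a Cycle 2 Day 1 start with dosing on Day 1 only

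*Combined protocol and SAP*

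**What the plan says.** The schedule is set out consistently in the places that define dosing. Section 5.3 specifies "IV nivolumab at an initial dose of 480 mg Q4W commencing C2D1". Section 5.4.2 gives "480 mg via a 30-minute IV infusion on Day 1 of every 28-day cycle", with Cycle 2 Day 1 as the first infusion. Footnote y to Table 6 reads "Nivolumab administration will commence on Cycle 2 Day 1", and the nivolumab row of that table is marked only at Cycle 2 Day 1 and at Day 1 of Cycle 3 onward. The synopsis and Section 3.1.2 agree. Section 3.1.2 adds that rucaparib runs alone for one 28-day cycle first, to explore immune priming. Section 7.4.3 takes the Cycle 1 Day 28 biopsy "prior to commencement of IV study medication".

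Three visit descriptions in Section 7.4 say otherwise:

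- **7.4.1, Cycle 1 Day 1:** "IV nivolumab will be administered after the first dose of rucaparib", and further down "Nivolumab IV will be administered as described in the Pharmacy Manual".
- **7.4.2, Cycle 1 Day 15:** "IV nivolumab will be administered after rucaparib".
- **7.4.5, Cycle 2 Day 15:** the same sentence as 7.4.2.

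**The concern.** There are two separate conflicts. At Cycle 1 Day 1 and Cycle 1 Day 15 the visit text contradicts the start date of nivolumab. At Cycle 2 Day 15 nivolumab has already started, but the text contradicts the dosing day.

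The first conflict matters more, because the nivolumab-free cycle is part of the design. The screening and Cycle 1 Day 28 biopsies are compared to isolate the effect of rucaparib on the immune microenvironment (Section 7.5.6.1). That is the primary objective in Cohort A2 and an exploratory one in Cohort A1. Nivolumab given before the second biopsy would confound that patient's pair.

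The Cycle 2 Day 1 baseline would also no longer be free of nivolumab. It serves the pre-dose nivolumab PK and immunogenicity samples in Table 7 and the creatinine baseline in Table 4, footnote 11. Section 1.2.2 relies on laboratory values after rucaparib alone to guide management of adverse events on the combination.

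The Cycle 2 Day 15 sentence cannot touch the run-in or the biopsy. Followed literally, it adds an infusion 14 days after the previous one.

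**Working it through.** The protocol states no figure to reproduce here. The check is a comparison of text, followed by simple arithmetic on what a literal reading would deliver.

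**Visit by visit**

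| Visit | Section 7.4 narrative | Nivolumab in the visit's procedure list | Table 6 |
|---|---|---|---|
| Cycle 1 Day 1 (7.4.1) | given | no | not marked |
| Cycle 1 Day 15 (7.4.2) | given | no | not marked |
| Cycle 2 Day 1 (7.4.4) | given | yes | marked |
| Cycle 2 Day 15 (7.4.5) | given | no | not marked |
| Day 1, Cycle 3 onward (7.4.6) | given | yes | marked |

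The wording in 7.4.2 and 7.4.5 is the same as in 7.4.4, where it plainly means an infusion at that visit. The wording in 7.4.1 could be stretched to mean some later time, but it stands in the Cycle 1 Day 1 instructions. No harmless reading covers all three visits. The missing items in the three procedure lists suggest that the sentences were carried over from the Day 1 visits.

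**Doses under a literal reading** (480 mg per infusion, Section 5.4.2)

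- Before the Cycle 1 Day 28 biopsy: planned 0; literal up to 2, so 2 × 480 = 960 mg.
- Through Cycle 2 Day 15: planned 1 × 480 = 480 mg; literal 4 × 480 = 1,920 mg.
- Interval over that period: 14 days instead of 28.

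**Nivolumab remaining at Cycle 1 Day 28**

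Section 1.1.3.3.1 gives a geometric mean half-life of 25 days. I assume simple one-compartment elimination, so the fraction remaining after *d* days is 2^(−d/25).

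- Cycle 1 Day 1 dose, 27 days earlier: 2^(−27/25) = 0.473, and 0.473 × 480 = 227 mg.
- Cycle 1 Day 15 dose, 13 days earlier: 2^(−13/25) = 0.697, and 0.697 × 480 = 335 mg.
- Both doses: 227 + 335 = 562 mg.

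The half-life varies between patients. The same formula for both doses gives:

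| Assumed half-life (days) | Remaining at Cycle 1 Day 28 (mg) |
|---|---|
| 13 | 354 |
| 15 | 401 |
| 25 | 562 |
| 40 | 684 |
| 50 | 731 |

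The 13 and 50 day rows are about one standard deviation either side of 25 days. They take the protocol's coefficient of variation of 77.5% and assume a log-normal distribution: σ = √ln(1 + 0.775²) = 0.686, e^0.686 = 1.99, 25/1.99 ≈ 13 and 25 × 1.99 ≈ 50. Across this range, exposure at the biopsy is substantial.

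**Share of the comparison affected**

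Cohort A2 plans about 10 patients, so one affected patient is 1 of at most 10 pairs, or 10%. The share is larger if some second biopsies are contraindicated. Pairs from other patients stand.

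**The case against.** The strongest reply is that the governing text is unanimous. Every section that defines dosing, with Tables 6 and 7, points to Cycle 2 Day 1, and a site reading in order meets Section 7.4.3 straight after 7.4.2. Nivolumab is assigned through the IRT system (Section 5.4), so an infusion in Cycle 1 would need supply outside the schedule. Section 10.9.1 already requires deviations to be recorded and allows a patient to be treated as nonevaluable. On this view the point is editorial.

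Much of that is fair. The intent is not in doubt, and a mis-dosed patient is unlikely. Several narrower points also stand:

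- The Pharmacy Manual sentence in 7.4.1 says how nivolumab is given, not when. By itself it contradicts nothing, but at that visit it reinforces the wrong instruction.
- The renal algorithm in Appendix 6 takes the creatinine baseline before the first infusion, so for a patient infused in Cycle 1 that baseline would still be nivolumab-free. Only the Table 4 baseline would be affected, and the two would then disagree.
- The milligrams remaining at biopsy do not drive the decision, since any nivolumab before the biopsy confounds that pair.

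The reply does not remove the error. The protocol does not say that the IRT system enforces visit timing. Section 7.4 is the text a site follows at each visit, and Section 10.9.1 tells investigators not to deviate from a protocol that here contradicts itself.

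**Conclusion.** The concern holds, with high confidence, and should be fixed. Three visit descriptions direct an infusion on days when none is planned: two conflict with the start date and one with the dosing day.

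The consequence is conditional on a site following the sentences literally, and the documents do not show that any did. The residual amount at biopsy (562 mg at the 25-day half-life) rests on the one-compartment assumption. The Simon two-stage figures for Cohort A1 are unaffected.

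**What to change.** In the next amendment:

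1. Delete the nivolumab statement from 7.4.1, 7.4.2 and 7.4.5. In 7.4.1 it is the closing clause of the opening sentence.
2. Delete the Pharmacy Manual sentence on nivolumab from 7.4.1.
3. Keep both sentences in 7.4.4 and 7.4.6, where they are correct.

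Meanwhile, write to sites that nivolumab is given on Day 1 only, from Cycle 2. State in the analysis plan that if a patient received nivolumab before the Cycle 1 Day 28 sample, that biopsy pair is left out of the rucaparib-only comparison.

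The cost is four short deletions, one letter and one line in the analysis plan. Design, sample size and data collection do not change.
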